5.5.2.2.2. ALT

Change from baseline in ALT over time will be analyzed using similar MMRM as described in Section 5.5.2.2.1 using baseline ALT (continuous) as covariate. The LS mean of change from baseline, standard error (SE), 95% CI and p-values will be provided.

5.5.2.2.3. HBsAg, HBeAg and HBV DNA

5.5.2.2.3.1. Change from Baseline to Nadir

The following change from baseline value to nadir values (JNJ3989 on-treatment and overall, respectively, as described in Section 5.5) in HBsAg, HBeAg (only for HBeAg-positive participants at screening) and HBV DNA will be summarized descriptively and box plots of the changes to nadirs in each blood marker will display the distribution.

5.5.2.2.3.2. Change from Baseline Over Time

Descriptive statistics on actual values (original unit and log₁₀ transformed values) and changes from baseline (log₁₀ transformed values) over time in each HBV blood marker will be summarized.

For HBsAg and HBV DNA, respectively, the comparison between intervention arms to leverage the longitudinal data during the DB study intervention phase will be done using similar MMRM as described in Section 5.5.2.2.1 using baseline value (quantitative) as covariate.

Waterfall plots for changes from baseline of HBsAg, HBeAg, and HBV DNA will also be presented by intervention arm at selected timepoints: Week 48, 72, 96, 120 and 144 (for Study Part 2).

5.5.2.2.3.3. Qualitative versus Quantitative Values

Cross-tabulations overtime of quantitative versus qualitative HBsAg and HBeAg values, respectively, will also be presented.

5.5.2.2.4. Liver Stiffness Measurement

The change from baseline in LSM will be compared between intervention arms at Week 48 using ANCOVA with intervention arm, randomization stratification factors as main effects in the model and baseline score as covariate.

At each assessment time point, a frequency distribution of severity scores will be produced. A graphical display will also illustrate the findings. In addition, a waterfall plot will be produced to display the individual changes from baseline in LSM.

5.5.2.3. Time to Event Endpoints

The Kaplan-Meier method will be used to estimate and plot the cumulative incidence by each intervention arm. The log-rank test will be performed to compare the intervention arms. The median time with 95% CI will be estimated using Kaplan-Meier method. This analysis method will apply to all time-to-events variables defined in Section 5.5.1.3.

5.6. Exploratory Endpoints

All exploratory endpoints will be summarized descriptively by intervention arm, phase, time point and study part. No imputation rule will be used in case of missing data and the analysis will be based on observed cases.

5.6.1. Definitions

5.6.1.1. Binary Endpoints

5.6.1.1.1. HDV RNA Decline and Normal ALT

All endpoints described in Section 5.5.1.1.1 which include HDV RNA TND will be evaluated by replacing TND by < LLOQ for assay sensitivity purpose:

- HDV RNA $\geq 2 \log_{10}$ IU/mL decline from baseline or < LLOQ in combination with normal ALT.
- HDV RNA $\geq 2 \log_{10}$ IU/mL decline from baseline or HDV RNA < LLOQ.
- HDV RNA < LLOQ in combination with Normal ALT.
- HDV RNA < LLOQ.

Additionally, some of the HDV RNA endpoints above may also be evaluated using the exploratory imputation rules defined in [Table 4](#).

Those endpoints will be analyzed as observed case without imputation (for combined endpoints, in case one of the two individual parameters is missing for a specific timepoint, the endpoint will be considered missing for this timepoint).

5.6.1.1.2. HDV RNA Cutoffs

HDV RNA will be evaluated when assessed at the following time points:

- 12 weeks after stopping JNJ-3989 (regardless of continuing NA treatment and when JNJ-3989 was stopped) without restarting JNJ-3989 treatment,
- 24 weeks after stopping JNJ-3989 (regardless of continuing NA treatment and when JNJ-3989 was stopped) without restarting JNJ-3989 treatment,
- 36 weeks after stopping JNJ-3989 (regardless of continuing NA treatment and when JNJ-3989 was stopped) without restarting JNJ-3989 treatment,
- 48 weeks after stopping JNJ-3989 (regardless of continuing NA treatment and when JNJ-3989 was stopped) without restarting JNJ-3989 treatment,

For each timepoint, the following cutoffs on actual values will be evaluated:

- LLOQ
 - <LLOQ TND
 - <LLOQ TD
- > LLOQ
- < 100 IU/mL
- < 2,000 IU/mL

5.6.1.1.3. HBV RNA and HBcrAg

The cutoffs for HBV RNA level are as follows:

- < LOD
- < LLOQ

The cutoffs for HBV RNA change from baseline are as follows:

- decrease by $\geq 1 \log_{10}$ IU/mL
- decrease by $\geq 2 \log_{10}$ IU/mL
- decrease by $\geq 3 \log_{10}$ IU/mL

The cutoffs for HBcrAg level are as follows:

- <3.0 \log_{10} U/mL
- <4.0 \log_{10} U/mL

The cutoffs for HBcrAg change from baseline are as follows:

- decrease by $\geq 1 \log_{10}$ IU/mL
- decrease by $\geq 2 \log_{10}$ IU/mL
- decrease by $\geq 3 \log_{10}$ IU/mL
- decrease by $\geq 4 \log_{10}$ IU/mL

5.6.1.1.4. HBV DNA Cutoffs

HBV DNA <LLOQ will be also evaluated when assessed at the following time points:

- 12 weeks after stopping JNJ-3989 (regardless of continuing NA treatment and when JNJ-3989 was stopped) without restarting JNJ-3989 treatment, 24 weeks after stopping JNJ-3989 (regardless of continuing NA treatment and when JNJ-3989 was stopped) without restarting JNJ-3989 treatment,
- 36 weeks after stopping JNJ-3989 (regardless of continuing NA treatment and when JNJ-3989 was stopped) without restarting JNJ-3989 treatment, 48 weeks after stopping JNJ-3989 (regardless of continuing NA treatment and when JNJ-3989 was stopped) without restarting JNJ-3989 treatment

5.6.1.1.5. HBsAg Seroclearance

Participants achieving HBsAg seroclearance (HBsAg <LLOQ) will be evaluated when HBsAg assessed at the following time points:

- 12 weeks after stopping JNJ-3989 (regardless of continuing NA treatment and when JNJ-3989 was stopped) without restarting JNJ-3989 treatment, 24 weeks after stopping JNJ-3989 (regardless of continuing NA treatment and when JNJ-3989 was stopped) without restarting JNJ-3989 treatment, 36 weeks after stopping JNJ-3989 (regardless of continuing NA treatment and when JNJ-3989 was stopped) without restarting JNJ-3989 treatment, 48 weeks after

stopping JNJ-3989 (regardless of continuing NA treatment and when JNJ-3989 was stopped) without restarting JNJ-3989 treatment,

5.6.1.2. Value and Change Over Time

Change from baseline is defined as the value at a given time point minus the baseline value.

Actual values (original unit and \log_{10} transformed values, where applicable) and changes from baseline (\log_{10} transformed values, where applicable) over time will be summarized by intervention arm and phase for the following variable:

- HBV RNA (original unit and \log_{10} transformed)
- HBcrAg (original unit and \log_{10} transformed)
- Anti-HBs antibodies

5.6.1.3. Time to Event Endpoints

The analyses will be performed if at least 10% of the participants experience the events.

5.6.1.3.1. Time to Undetectability of HBcrAg

The same derivation and censoring rules as in Section 5.5.1.3.1.1 apply for the time to undetectability of HBcrAg, which will be calculated using the date of first HBcrAg TND.

Only the participants with HBcrAg values \geq LLOQ+ 0.5 \log_{10} U/mL (i.e. $\geq 3.5 \log_{10}$ U/mL) at baseline will be included in this analysis.

5.6.1.3.2. Time to Appearance of Anti-HBs Antibodies

Appearance of anti-HBs antibodies is defined as a baseline anti-HBs (quantitative) $<$ LLOQ and a post-baseline assessment \geq LLOQ.

The same derivation and censoring rules as in Section 5.5.1.3.1.1 apply for the time to appearance of anti-HBs antibodies, which will be calculated using the date of first appearance as defined above.

5.6.1.3.3. Time to Appearance of Anti-HBe Antibodies

Appearance of anti-HBe antibodies is defined as a baseline anti-HBe antibodies (qualitative) with a "NEGATIVE" result and a post-baseline assessment with "POSITIVE" result.

The same derivation and censoring rules as in Section 5.5.1.3.1.1 apply for the time to appearance of anti-HBe antibodies, which will be calculated using the date of first appearance as defined above.

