5.5.1.1.8. HBsAg Seroconversion

Seroconversion of HBsAg is defined as having achieved HBsAg seroclearance and appearance of anti-HBs antibodies.

The seroconversion will only be assessed at the time points when the anti-HBs antibodies assessment is available. If the HBsAg value is missing at that specific time point, then the non-missing lab test closest to that specific timepoint will be used. If the non-missing lab test before and after the specific timepoint fall equidistant from the target timepoint, the later one will be used to impute the missing value.

Appearance of anti-HBs antibodies is defined as a baseline anti-HBs antibodies (quantitative) <LLOQ and a post-baseline assessment \geq LLOQ. A sensitivity analysis will be conducted using the threshold of 10 mIU/mL, i.e. appearance of anti-HBs antibodies is defined as a baseline anti-HBs antibodies (quantitative) <10 mIU/mL and a post-baseline assessment \geq 10 mIU/mL.

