5.6.2.2.2. Anti-HBs Antibodies

For participants with positive anti-HBs antibodies at baseline who will reach HBsAg seroclearance (as defined in Section 5.4.3.1), descriptive statistics will be calculated for the change (increase) of anti-HBs antibodies level from baseline at the timepoint when achieving the HBsAg seroclearance by intervention arm. In an additional summary, the change of anti-HBs antibodies level from baseline at Week 48 will be summarized descriptively for the subset of the participants achieving HBsAg seroclearance at any time before or at that given timepoint by intervention arm.

If available, cross-tabulations overtime of quantitative versus qualitative anti-HBs values, respectively, will also be presented.

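### Time to appearance of anti-HBs and of anti-HBe is not limited to participants who are antibody-negative at baseline, so as written the Kaplan-Meier incidence is diluted by those who cannot have the event

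*SAP*

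**What the plan says.** Three exploratory time-to-event endpoints stand together in SAP 5.6.1.3.

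- **HBcrAg (5.6.1.3.1).** Only participants at least 0.5 log10 above the LLOQ "at baseline will be included in this analysis".
- **Anti-HBs (5.6.1.3.2).** The event needs a baseline value below LLOQ and a later value at or above it. "The same derivation and censoring rules as in Section 5.5.1.3.1.1 apply for the time to appearance of anti-HBs antibodies". No baseline restriction follows.
- **Anti-HBe (5.6.1.3.3).** The event needs a negative baseline result and a later positive one. "The same derivation and censoring rules as in Section 5.5.1.3.1.1 apply for the time to appearance of anti-HBe antibodies". Again no baseline restriction follows.

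Section 5.5.1.3.1.1 censors anyone who has not had the event at the last HDV RNA assessment or the cut-off date, whichever is earlier. Section 5 makes ITT the default efficacy set. Sections 5.6.2.3 and 5.5.2.3 call for Kaplan-Meier curves, medians and log-rank tests. A run rule heads 5.6.1.3: "The analyses will be performed if at least 10% of the participants experience the events".

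The anti-HBs condition also enters a secondary endpoint in 5.5.1.1.8: "Seroconversion of HBsAg is defined as having achieved HBsAg seroclearance and appearance of anti-HBs antibodies". Section 5.5.1.1 asks for the number and proportion of participants with that endpoint and sets no at-risk denominator.

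**The concern.** A time-to-event analysis should count as at risk only people who can have the event. Here the definition rules it out for anyone antibody-positive at baseline, and nothing in the text removes them. The curve then mixes two quantities: how often the antibody appears in those who lack it, and how many already had it.

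The SAP expects such participants. Section 4.2.1 tabulates baseline anti-HBe as positive, negative or borderline, and baseline anti-HBs as below or at/above 10 mIU/mL. Section 5.6.2.2.2 plans a summary that begins "For participants with positive anti-HBs antibodies at baseline who will reach HBsAg seroclearance".

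The incidence and the median are at stake, and so is whether the 10% rule lets the analysis run, because that rule does not say which participants make up its denominator. There is also a smaller slip. Taken literally, the imported rule censors an antibody endpoint at the last HDV RNA assessment.

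**Working it through.** The SAP gives no event count or power for these endpoints, so there is no figure to reproduce.

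**Inputs from the SAP.** N = 30 in Part 2 and N = 52 in the whole study (1.2); the 10% rule (5.6.1.3); ITT default (5); censoring of non-achievers (5.5.1.3.1.1).

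**Assumed, because the SAP gives neither.** f, the share antibody-positive at baseline, is shown from 0.1 to 0.7 and need not be the same for the two antibodies. p, the event rate among those negative at baseline, is set at 20%.

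**1. Dilution.** If baseline-positive participants stay in and never have the event, then with complete follow-up

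reported incidence = p × (1 - f).

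For p = 20%:
- f = 0.1: 0.20 × 0.90 = 18%
- f = 0.25: 0.20 × 0.75 = 15%
- f = 0.5: 0.20 × 0.50 = 10%
- f = 0.7: 0.20 × 0.30 = 6%

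**2. Median.** Even if every participant at risk has the event, cumulative incidence stops at 1 - f. For f > 0.5 this is below 50%, so no median exists whatever the treatment does.

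**3. Run rule.** Counted on all participants, the rule needs 3 events (10% of 30) or 6 events (10% of 52 is 5.2, rounded up). Counted on the m participants at risk, it needs 10% of m, rounded up. The chance of running is the binomial probability of at least that many events among m people at p = 20%.

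| N | f | m at risk | events needed, all | chance of running | events needed, at risk | chance of running |
|---|---|---|---|---|---|---|
| 30 | 0.1 | 27 | 3 | 93% | 3 | 93% |
| 30 | 0.25 | 22 | 3 | 85% | 3 | 85% |
| 30 | 0.5 | 15 | 3 | 60% | 2 | 83% |
| 30 | 0.7 | 9 | 3 | 26% | 1 | 87% |
| 52 | 0.1 | 47 | 6 | 93% | 5 | 97% |
| 52 | 0.25 | 39 | 6 | 82% | 4 | 97% |
| 52 | 0.5 | 26 | 6 | 42% | 3 | 92% |
| 52 | 0.7 | 16 | 6 | 8% | 2 | 86% |

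The choice of denominator matters little at low f and a great deal at high f. The at-risk figures need care: at N = 30 and f = 0.7 one event is enough, and 87% is simply 1 - 0.8^9, the chance of at least one event in nine people.

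**The case against.** The SAP nowhere states that baseline-positive participants are kept. That follows from silence, the ITT default and the borrowed censoring rule, and a programmer could take the baseline condition in the definition as an eligibility filter. This is fair, and it makes the matter a gap in specification, not a stated error. The HBcrAg paragraph weakens the defence, since there the restriction is written out. If both readings are possible, two programmers can produce different curves from the same plan.

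Three stronger inferences are tempting but not supported:

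- **That the 10% rule can cancel HBsAg seroconversion.** The rule stands under 5.6.1.3 and covers only the exploratory time-to-event endpoints. Seroconversion is a binary other secondary endpoint with no run rule. Its proportion among all treated, randomised participants is a legitimate estimand.
- **That the log-rank comparison is invalid.** Antibody status at baseline precedes randomisation. Participants who cannot have the event lower the incidence in both arms but do not invalidate the test under the null.
- **That the information would be lost.** Section 5.6.2.2.3 plans anti-HBe counts and shift tables from baseline with no run rule, so negative-to-positive changes would still be visible. Section 5.5.2.1.3 summarises anti-HBs appearance without seroclearance.

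Moving the 10% rule to the at-risk set also has a price. Counting on all 30 participants keeps a floor of three events, while the at-risk count can fall to one.

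**Conclusion.** The point holds for the two time-to-appearance analyses. As written, baseline-positive participants remain at risk as certain non-events, incidence is multiplied by about (1-f), and the median is out of reach once f exceeds 0.5. The factor is exact with complete follow-up and approximate otherwise. Its size depends wholly on f, which the SAP does not give: at f = 0.1 the effect is slight (20% becomes 18%), and at f = 0.7 it is large (20% becomes 6%).

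For seroconversion the point is narrower. A participant with anti-HBs at or above LLOQ at baseline who clears HBsAg always counts as not seroconverted, so a second denominator would help the reader, but the ITT proportion is not wrong. Time to antibody appearance is not among the endpoints listed in 1.1, the study is now descriptive, and no primary or key secondary analysis is touched.

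**What to change.** 1. In 5.6.1.3.2, include only participants with baseline anti-HBs below LLOQ. In 5.6.1.3.3, include only those with a negative baseline anti-HBe. The HBcrAg sentence in 5.6.1.3.1 is the model. State that borderline anti-HBe baselines are outside this set, and say how missing baselines are handled.
2. In both sections, censor at the last anti-HBs or anti-HBe assessment, respectively, in place of the last HDV RNA assessment.
3. State that for these two endpoints the 10% rule refers to the at-risk set. Note that with few at risk this may mean a single event, and that counts are then reported descriptively.
4. For HBsAg seroconversion, keep the ITT proportion. Add as a supplement the proportion among participants with baseline anti-HBs below LLOQ (below 10 mIU/mL for the sensitivity threshold).

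The cost is a few sentences, a baseline population flag and one supplementary table column. Denominators become smaller and intervals wider.

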5.6.1.4. Relationship between HBsAg and HDV RNA

HBsAg levels and decline from baseline (in \log_{10} transformed values) and HDV RNA levels and change from baseline (in \log_{10} transformed values) during study intervention and follow-up will be used to analyze a potential relationship between the two markers.

In case either HBsAg or HDV RNA is missing at a specific timepoint, no imputation will be performed.

Correlations between HBsAg and HDV RNA markers may be evaluated. The list of HBsAg and HDV RNA endpoints, including but not limited to, are defined below. Note, that these analyses may be performed if sufficient data are collected on patients and will only be performed at a later time point in a post hoc nature.

Off-Treatment Clinical HDV Flares (Yes/No)	
 • HBsAg value and change from baseline (absolute and log₁₀ values) at End of Treatment of JNJ-3989. • HBsAg seroclearance at End of Treatment of JNJ-3989- . (Yes/No)
--	---

5.6.1.5. Relationship Between Baseline characteristics and Efficacy Endpoints

The relationship between efficacy endpoints at Week 48 and selected baseline characteristics defined in the list of subgroup variables for efficacy (see Section 2.4.1) will be evaluated as part of the subgroup analyses in Sections 5.3.3 and 5.4.5. In addition, an analysis of correlation at Week 48 will be performed to evaluate the relationship between endpoints at Week 48 (HDV RNA decline from baseline, change from baseline in ALT, change in HBsAg, change in LSM) and selected baseline characteristics. This analysis will use continuous variables only. More details are provided in Section 5.6.2.5.

In addition, the relationship between efficacy endpoints and on-treatment predictive outcomes at early visits (such as HDV RNA reduction ≥ 2 log₁₀ from baseline, normal ALT, LSM reduction, HBsAg seroclearance etc) will also be explored.

5.6.1.6. Liver Viral Response

In case a sufficient number of participants agrees to undergo the optional liver biopsy at baseline and/or Week 24, the following endpoints will be evaluated:

- Change from baseline at Week 24 in intrahepatic HDV RNA (semi-quantitative: negative, low, middle, high expression)
- Change from baseline at Week 24 in intrahepatic HDAg (semi-quantitative: negative, low, middle, high expression)
- Change from baseline at Week 24 in number and proportion of pgRNA-positive hepatocytes
- Change from baseline at Week 24 in number and proportion of HBsAg-positive hepatocytes
- Change from baseline at Week 24 in number and proportion of silent hepatocytes
- Change from baseline at Week 24 in pgRNA levels (copies/cell)
- Change from baseline at Week 24 in intrahepatic HBsAg (semi-quantitative: negative, low, middle, high expression)

- Change from baseline at Week 24 in intrahepatic HBV RNA (semi-quantitative: negative, low, middle, high expression)

Additional endpoints may be added if sufficient biopsy data are available for the analysis.

5.6.1.7. **Liver Immune Response**

In case a sufficient number of participants agrees to undergo the optional liver biopsy at baseline and/or Week 24, the following immune cells may be evaluated:

- CD45 positive cells,
- CD4 positive cells,
- CD8 positive cells,
- Natural Killer (NK) cells,
- T-cells,
- Dendritic cells

5.6.1.8. **Relationship Between On-Treatment ALT Elevations, Efficacy and Safety Endpoints, and Baseline Characteristics**

The relationship between On-Treatment ALT elevations will be evaluated. The following relationships will be evaluated:

- Efficacy outcomes by ALT Elevation Status: HBsAg, HBeAg, HDV RNA, HBV DNA, HBcrAg, Liver stiffness measurement
- Safety outcomes by ALT/AST Elevation Status: Direct Bilirubin, Total Bilirubin, Individual GFR, Platelets, Cholesterol, INR (ratio), Hemoglobin, Eosinophils, Albumin, LDH, Prothrombin time, Alkaline Phosphatase, GGT, Alpha Fetoprotein,
- Tables of ALT elevation status by HBsAg, HBeAg, HDV RNA, HBV DNA, HBV RNA, type of NA, race, BMI, age, anti-HDV IgM, Fibroscan at Baseline
- ALT values over time by HBsAg, HBeAg, HDV RNA, HBV DNA, HBV RNA, type of NA or none, race, BMI, age, anti-HDV IgM, Fibroscan at Baseline (Cut-offs or Categories)

5.6.2. **Analysis Methods**

5.6.2.1. **Binary Endpoints**

Descriptive summaries including 95% CI and graphical displays will be provided for the exploratory binary endpoints.

5.6.2.1.1. **HDV RNA Cutoffs**

The proportion of participants with HDV RNA $<$ or \geq cutoffs defined in Section 5.6.1.1.2 will be evaluated at each of the following off-treatment time points: 12, 24, 36 and 48 weeks, respectively, after stopping JNJ-3989.

In an additional summary, these proportions will be calculated with the denominator including only those participants who have reached the off-treatment time points (week 12, 24, 36 or 48) and have stopped JNJ-3989 and have not restarted JNJ-3989, regardless of continuing NA treatment prior to the time point of interest

5.6.2.1.2. HBsAg Seroclearance

The proportion of participants achieving HBsAg seroclearance will be evaluated at each of the following off-treatment time points: 12, 24, 36 and 48 weeks, respectively, after stopping all study interventions and without restarting JNJ-3989.

In an additional summary, these proportions will be calculated with the denominator including only those participants who have reached the off-treatment time points (week 12, 24, 36 or 48) and have stopped JNJ-3989 and have not restarted JNJ-3989, regardless of continuing NA treatment prior to the time point of interest.

5.6.2.2. Value and Change Over Time

Similar summaries and graphical displays as described in Section 5.5.2.2 will be provided for the exploratory continuous endpoints.

Subsections below describe the additional analyses specific to individual continuous exploratory endpoints.

5.6.2.2.1. HBV RNA and HBcrAg

HBcrAg will be summarized by NA treatment history (Yes/No) and overall, while HBV RNA will only be summarized by NA treatment history.

The values of and changes from baseline in HBV RNA and HBcrAg, respectively, will be summarized only descriptively over time in a similar manner as for values and changes from baseline over time in HBsAg, HBeAg, and HBV DNA as described in Section 5.5.2.2.3, including the change from baseline value to nadir values (both on and off treatment) and the various graphical displays.

Waterfall plots for changes from baseline in HBV RNA and HBcrAg will also be presented.

